Infants with birth weight 750-1000 grams are NPO for 7 days followed by initiation of priming feed of 1 ml every 2 hours for 7 days, after which feeds are increased by 0.5 ml/feed daily until they reach 100 ml/kg/day. They then increase by 10 ml/kg/day until they reach full feeds of 150 ml/kg/day.

Infants with birth weight 1001-1250 grams are NPO for 4 days followed by initiation of priming feeds of 1.5 ml every 2 hours for 4 days, after which feeds are increased by 1 ml/feed every other day until 100 ml/kg/day. They then increase by 10 ml/kg/day until they reach full feeds of 150 ml/kg/day.

Infants with birth weight 1251-1500 grams are NPO for 1 day followed by priming feeds of 2 ml for 2 days, after which they increase by 20 ml/kg/day until they reach full feeds of 150 ml/kg/day.

Once enteral feeds reach 50 ml/kg/day MBM is fortified with 1 packet of human milk fortifier for every 50 ml of breast milk. Then at 75 ml/kg/day MBM is fortified with 1 packet of human milk fortifier for every 25 ml of breast milk.

As enteral feedings are advanced the total parenteral nutrition is gradually decreased. The control group will have TPN and SMOF lipid adjusted per NICU guidelines and standard practice until full enteral feeds are achieved. The protein provided in TPN is adjusted based on volume being given and what will fit inside the TPN due to concentration, and lipids are usually decreased by 50% when the enteral nutrition is providing 75 ml/kg/day, and then discontinued with enteral nutrition is providing 100 ml/kg/day. The intervention group will have protein content of the TPN and SMOF lipid adjusted dependent on the breast milk composition- goal 4g/kg/day protein, 100-130kcal/kg/day.

This study will be a randomized control trial with 2 arms. Patients will be randomized to either the control group (standard fortification) or intervention group (targeted fortification) in a 1:1 allocation ratio. Twins will be considered as one and allocated to the same group. Allocation group will be stratified to four groups according to birth weight: <750g, 751-1000g, 1001-1250g, 1251-1500g. This stratification is based upon our NICU feeding guideline, and will ensure that enrolled infants will receive comparable nutrition progression (e.g. NPO days, days of trophic feeds) throughout the study period. The allocation will be concealed in a sequentially numbered, opaque, sealed envelope, that will be opened after consent is obtained. After randomization, the groups will not be blinded to the investigators or caregivers.

All VLBW infants whose mothers consent to provide breast milk and participate in the study will be included. In the control group, breast milk will be fortified per protocol as listed above and TPN weaned per NICU guideline. The intervention group will receive standard fortification with additional added liquid protein to provide 4 g/kg/day and microlipid to provide 100-130 kcal/kg/day once 100 ml/kg/day of enteral feeds are achieved. Once the infants reach goal enteral feeds of 150ml/kg/day they will continue on the standard or targeted fortification for 4 weeks.

The mothers will provide breast milk when they come to visit their infant in the NICU. They will have access to a pump while visiting in the NICU and lactation consultant will help to arrange for a pump to use at home. They will be provided containers to collect breast milk at home to bring in when they visit their baby in the NICU. Once weekly the mother will collect the previous 24 hours supply of breast milk, which will be homogenized and a sample taken for analysis. The sample will then be analyzed for composition using the Miris human milk analyzer for the carbohydrate, fat, and protein content and caloric density. The remainder of

If this field is not completed your protocol will not be reviewed. Do not enter N/A. Please describe what methods and procedures will be involved in this research.

the milk will be stored as a batch and labelled to feed the infant when he/she is ready.

In the NICU a work area has been identified which has a sink, storage area, and work surface. The work surface will be cleansed with a sterilization cloth, followed by handwashing and then retrieving the milk from the refrigerator using universal precautions. The 24 hour supply will be mixed into one clean mixing bottle large enough to accommodate the entire 24 hours supply. It will be homogenized by inverting the bottle 10 times. A 10 ml aliquot of the sample will be transferred into a container labeled with subject number and taken for analysis. The remainder of the milk will be repackaged into containers and labeled as one batch. The Miris human milk analyzer is a mid infrared that reports the amount of energy absorbed at each wavelength. The amount of fat (grams), lactose (grams), total protein (grams), true protein (grams), and energy (kcal) per 100 ml will be reported. The milk will be then fortified per protocol (control group), or with targeted fortification (intervention group) as described above.

In the NICU infants are weighed on a daily basis, as clinical condition allows; weekly head circumference, length, and either flank skin fold or mid upper arm circumference (dependent on weight). As standard of care infants <1500 g at birth have a PEAPOD measurement prior to discharge to evaluate body composition. The measurements will be performed by nursing staff on routine basis and will not be blinded to the group assignment, as the bedside nurse will also likely be assisting in preparing the feeds for the infant. The Peapod assessment is performed by CRU staff as standard of care for these patients prior to discharge, they will be blinded to the group assignment but the NICU staff (nursing, nurse practitioner, or fellow) accompanying the patient to the measurement will not be blinded.

8.5 Does this study only involve the use of existing/retrospective data/specimens?
No

Check yes or no.

8.6 Describe in detail the study design also known as the experimental flow. Include all study procedures a subject will go through, in order of sequence and timing, including frequency of visits, duration of visits, length of subject participation etc. Please Note this needs to be written for an educated person who is not an expert in the field, do not exceed 300 words:

This is also known as NIH Experimental Procedure section or Clinical Trial Procedure/Experimental Flow section. Do not just attach documents in response to this question you must do a study design summary for IRB Review.

- Infants with birth weight <1500g born at MetroHealth will be identified and are eligible for this study if they meet inclusion and exclusion criteria. Mothers of these infants will be approached for recruitment and included if they consent to participate

- As standard NICU procedure these infants will be started on total parenteral nutrition (TPN) with SMOF lipids, and delayed initiation of enteral feeds determined by birth weight and NICU guideline

- The infant will be randomized to the standard fortification group (control) or targeted fortification group (intervention).

o Standard fortification group (control)

Breast milk will be fortified standard with Similac Human Milk Fortifier 1 packet: 50 ml breast milk at 50ml/kg/day enteral feeds, then 1 packet:25 ml breast milk at 75 ml/kg/day

As feedings are advanced to goal of 150 ml/kg/day, the TPN and SMOF lipids will be decreased per standard management and NICU guidelines

o Targeted fortification group (intervention)

Breast milk will be fortified standard with Similac Human Milk Fortifier 1 packet: 50 ml breast milk at 50ml/kg/day enteral feeds, then 1 packet:25 ml breast milk at 75 ml/kg/day

During this time, as the volume decreases, the TPN and SMOF lipids will be optimized to provide a goal of 4 g/kg/day of protein, and 100-130kcal/kg/day

At 100 ml/kg/day of enteral feeds additional liquid protein and/or microlipids will be added to the breast milk to provide goal of 4 g/kg/day of protein and 100-130 kcal/kg/day. This will be determined by analysis of the milk and reported composition.

They will continue targeted fortification for 4 weeks after achieving full feeds of 150 ml/kg/day

- Breast milk analysis will occur on a weekly basis immediately after birth for all infants enrolled in the study.

- Mothers collect a 24hr supply of breast milk once per week, from which a study team member will obtain a 10 ml representative sample for analysis. The 24hr collection of breast milk will be mixed into a clean container that can accommodate the entire volume. It will be homogenized and a 10 ml sample removed for

analysis. The remaining breast milk will be repackaged and placed back into the refrigerator in the NICU.

- After analysis, the milk for the following 1 week will be labeled and batched together
- For donor breast milk, each 'lot' will be analyzed and labeled for future use
- Analysis will take place at MetroHealth in the lab, using the Miris human milk analyzer. The amount of fat (grams), lactose (grams), total protein (grams), true protein (grams), and energy (kcal) per 100 ml will be reported and used for calculations.
- Infants will have birth measurements obtained, daily weight, weekly anthropometric measurements, and body composition measurement prior to discharge. The measurements will take a few minutes to obtain on routine basis per NICU protocol. The Peapod (body composition) measurement will take approximately 20 minutes total traveling from the NICU to CRU and back, but the actual assessment takes 2-3 minutes. This will be done with the infant is medically stable and approaching discharge.

The subjects will be in the study from time of consent to 4 weeks following the achievement of full enteral feedings, which may range from 6 weeks to 12 weeks depending on the birth weight and the clinical status of the infant. The smallest babies will take the longest to increase to full feeds due to the slow feeding protocol.

8.7 Please attach study design/subject visit schedule here:

Name	Description
There are no items to display	

If you have an electronic schedule of study visits and/or procedures please attach here.

View: 09-00 Inclusion/Exclusion Criteria

9.0 Inclusion/Exclusion Criteria:

9.1 What are the inclusion criteria? Put this information in bullet form:

Premature infants <1500 g
Mother consenting to provide breast milk or use of donor breast milk

Please list inclusion criteria.

9.2 What are exclusion criteria? Put this information in bullet form:

Infants with major congenital malformations
Infants with medical conditions precluding them from having breast milk
Mothers with medical conditions that preclude them from providing breast milk
Insufficient breast milk supply
Refusal of donor breast milk

Please list exclusion criteria.

9.3 How will subject eligibility be determined and by whom?

The principal investigator and co-investigators will determine subject eligibility based on birth weight, inclusion, and exclusion criteria.

Please describe in detail.

9.4 Will you exclude women and minorities, or persons under 21 from enrollment?

No

Check yes or no.

9.5 If yes, which groups are you excluding? Provide justification for your decision.

List groups to be excluded then provide justification.

9.6 Attach Documents:

Name	Description
There are no items to display	

If you are unable to fit your answers in the text boxes provided please attach as a word document.

View: 10-00 Risk/Benefits

10.0 Assessment of Risk I:

10.1 Identify and distinguish between those procedures that are standard versus those that are experimental. Include the frequency and duration of each activity and the total length of subject participation:

Standard procedures: Pumping and providing expressed breast milk, documentation of baby demographics, weekly anthropometric measurements, PEAPOD prior to discharge, Metrohealth standard feeding protocol.

Please distinguish between those procedures that are standard versus those that are experimental. Describe in detail all experimental procedures.

Experimental procedure: Weekly analysis of small aliquot of breast milk with Miris mid infrared human milk analyzer, targeted fortification of breast milk to achieve protein goal of 4g/kg/day and calories 100-130 kcal/kg/day, fortification of breast milk specifically for each mother/infant.

Deviation from standard Metrohealth NICU practice: collection of 24 hour supply of breast milk, analysis of breast milk content, targeted individualized addition of protein and fat. All other procedures are the standard of practice in NICU.

The measurements will take a few minutes to obtain on routine basis per NICU protocol. The Peapod (body composition) measurement will take approximately 20 minutes total traveling from the NICU to CRU and back, but the actual assessment takes 2-3 minutes. This will be done with the infant is medically stable and approaching discharge. Analysis of the breast milk will take approximately 20 minutes per sample, including the time to prepare the sample for analysis and analysis using the Miris human milk analyzer.

The subjects will be in the study from time of consent to 4 weeks following the achievement of full enteral feedings, which may range from 6 weeks to 12 weeks depending on the birth weight and the clinical status of the infant. The smallest babies will take the longest to increase to full feeds due to the slow feeding protocol.

10.2 Describe any therapeutic alternatives to the research that may exist. How are they different from those procedures that subjects would normally undergo?

Therapeutic alternative is standard fortification of breast milk per protocol. This uses reported average protein and caloric content of breast milk and adds standard amounts of fortifier. Content of breast milk is variable between mothers and has wide range. They also have the option to not participate in the study and receive standard NICU management.

Describe any therapeutic alternatives. Can subjects receive this drug or device outside of a research study?

10.3 What are the outcome variables and how will they be analyzed? What are the statistical and analytical methods that will be used? Note this section can be copied from the NIH Grant Application or from the Statistical and Analytical Methods section of the industry trial protocol.

The outcome variables are the anthropometric measurements including daily weight; weekly length, head circumference, skin fold thickness or mid upper arm circumference; and PEAPOD body composition measurements prior to discharge.

Define outcomes and describe data analysis, please include a power calculation.

Our primary outcome is body composition, as measured by air displacement plethysmography (PEAPod). As standardized assessment of body composition is relatively new in the preterm infant population, we are using clinical judgment to determine that a difference in fat free mass z-score (from data from Norris T, 2019) of 0.5 is clinically significant. To detect a difference at alpha $\alpha=0.05$ with 80% power, 25 infants per group are required. This is a realistic goal for clinical enrollment, due to the historical MetroHealth NICU census composition. According to the census at MetroHealth, the total number of infants with birth weight less than 1500 g for 2016 was 81 infants, and in 2017 was 84 infants.

If the requested information does not fit in the text box please attach a word document.

10.4 If the above requested information does not fit in the text box please attach a word document here:

Name	Description
There are no items to display	

View: 10-01 Risk/Benefits

10.1 Assessment of Risk II:

10.5 List and quantitate the risks involved for each experimental procedure in bullet form. Identify risks as common (greater than 10%) uncommon (greater than 1% up to and including 10 %) rare (1% or less). This must match the risks listed in the Consent Form:

Targeted fortification- rare, some babies may have elevated BUN which is routinely monitored in the NICU, or rare, feeding intolerance

Select all that apply.

There is also risk of breach of confidentiality, but this is rare. Data will be stored securely, only key study investigators will have access to data, and it will be deidentified and only the PI will have access to the key.

The probability and magnitude of harm or discomfort anticipated in the

research are no greater than those ordinarily encountered daily during routine care while admitted to NICU.

10.6

Are there defined stopping rules? Yes No

Describe in enough detail for the IRB to assess safety.

What are the stopping rules for the study? What are the conditions under which a subject will be withdrawn from the study for safety reasons, i.e. disease progression?

Intolerance to fortification, excessive emesis or recurrent, otherwise unexplained, abdominal distention.

What findings, events, or conditions would require a research subject to be removed from the study? (i.e. disease progression)

Clinical worsening, acute decompensation of infant precluding them from receiving enteral feeds.

If a patient become acutely ill and significantly decompensates they may be removed from the study. Ex: sepsis, abdominal distention, blood in the stool, respiratory failure with increasing need for respiratory support. If a patient becomes comfort-care only and no longer receiving enteral feeds they may also be removed from the study.

10.7

What Category of risk will study participants be exposed too?

Name

[Privacy](#)

[Other](#)

Should be consistent with risks listed in the Consent Form.

10.8

If Other listed above please specify:

Infants will need to leave the NICU for PEAPOD body composition measurement. This will be done once they are determined to be medically stable and ready for discharge.

A text box is provided for further explanation.

A text box is provided for further explanation.

10.9

Describe the availability of medical or psychological services that participants might require as a consequence of participation in this the research:

The participants will have medical services available in the NICU at their disposal during the entirety of involvement in the study. Every effort will be made to obtain resources to support mother's pumping activities and providing of breast milk- pumping room with breast pumps and supplies, lactation services, nutrition services.

10.10

Describe in detail any measures in place to minimize or protect against the exposure of study subjects to these risks:

Infants will be transferred to the research unit in an open crib one hour after his/her regular feed. they will be placed on a warmer while heart rate, respiratory rate, and pulse ox will be monitored continuously. The entirety of the assessment will take about 20 minutes. After the PEAPOD is completed the infant will be transferred back to the NICU.

Discuss any provisions for intervention in the event of an Adverse Event i.e. stopping rules.

Data will be stored in a secure location to protect confidentiality.

10.11

Please add any documents related to the above questions:

Name	Description
There are no items to display	

If your answers to the above questions are too long for the space provided please attach them here.

View: 10-02 Risk/Benefits

10.2 Benefits:

10.12

Describe the potential benefits to the subject as a result of participating in this research. If there is no direct benefit to subjects please state that as well: *Note: payment or compensation to subjects for participation is not to be considered a potential benefit.*

Receiving targeted fortification may result in improved growth and body composition with more lean body mass. Improved neonatal growth may have

Describe potential benefits to the study subjects.

impact on improved long term medical outcomes, with decreased susceptibility to infections, and also neurodevelopmental outcomes.

- 10.13 Describe the potential benefits to society as result of this research: Care of premature infants has a large financial and emotional impact on parents and society, even after discharge from the NICU. They are high risk patients that may require frequent readmissions to the hospital with illnesses. Optimizing growth and nutrition of premature infants is associated with decreased morbidity and improved outcomes.**

Describe potential benefits to society.

If a significant difference can be shown in the study group, having a milk analyzer in all NICUs and targeted fortification of breast milk to provide optimal nutrition can become standard of care. This has the potential to reduce the burden on the health care systems taking care of these patients.

- 10.14 What is the risk/benefit ratio of the research?**

In this research, infants are given additional protein and fat targeted to their mother's breast milk composition and their nutritional needs, which alone does not have any potential risk. The benefit of improved growth is significant with overall improved medical and neurodevelopmental outcomes. Potential benefits outweigh the risk of participation.

Discuss why the risks are reasonable in relation to the anticipated benefits.

- 10.15 Attach Documents:**

Name	Description
There are no items to display	

Attach documents here.

View: 11-00 Study Participant Information I

11.0 Study Participant Information I:

- 11.1 How will the Principal Investigator assure he/she has access to a population that would allow recruitment of the required number of study participants (i.e. prep for research):**

Based on MetroHealth Medical Center NICU statistics, there are approximately 80 babies weighing less than 1500 grams admitted every year.

How does the PI know he/she has the required number of subjects?

The accrual numbers in 11.2 represent mother/baby couples.

- 11.2 Anticipated number of subjects (all sites): [enter a number]**

60

Please give the total # of subjects to be enrolled at all sites and anticipated subjects to be enrolled at MHS.

Anticipated number of subjects to be enrolled at MHS: [enter a number]

60

Anticipated number of potential subjects to be approached: [enter a number]

60

- 11.3 If this is a multi-site study, how many sites will there be? [enter a number]**

How many total sites?

- 11.4 Subject Characteristics:**

Subject Population Categories

[Inpatients](#)

Check all that apply

- 11.5 Subject Source:**

Subject Source Characteristics

[Other](#)

Check all that apply

11.6

If "other" list above in either 11.4 or 11.5 please describe:

Infants delivered at MHMC with birth weight less than 1500 grams on admission to NICU.

If applicable please describe.

View: 12-00 Study Participant Information II

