1.04 What is your eRA Commons Name?

eRA Commons Name required for all non- industry studies

1.05 Anticipated Start Date:
5/20/2019

Anticipated End Date:
3/31/2021

Anticipated Date Study to Begin (1st Patient)

Anticipated End Date

1.06 Approximate Inpatient Days Per Subject:
90

Enter approximate numbers

Approximate Outpatient Visits Per Subject:
0

1.07 *After August 2010 this is a read only copy of the paper CRU Resource Application:*

Old CRU Application forms

Name Version
 There are no items to display

1.08 These are your target enrollment numbers for the ethnic and racial categories below:

Enter anticipated numbers for this protocol

Ethnic Category

Ethnic Category	Sex/Gender		Total
	Females	Males	
Hispanic or Latino	5	5	10
Not Hispanic or Latino	25	25	50
Ethnic Category Total of All Subjects	30	30	60

Racial Category

Racial Category	Sex/Gender		Total
	Females	Males	
American Indian/Alaska Native	0	0	0
Asian	1	1	2
Native Hawaiian or Other Pacific Islander	0	0	0
Black or African American	17	17	34
White	12	12	24

Racial Categories Total of all Subjects 30 30 60

View: CRU 01-02 CRU Resource Needs

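### The 25 infants per group cannot be derived from the stated inputs: 80% power needs an unstated SD of about 0.62 or less (two-sided), and at an assumed SD of 1 power is about 41%

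*Combined protocol and SAP*

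**What the plan says.** The only sample-size statement is in section 10.3 of the combined protocol and SAP.

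- **Outcome:** "Our primary outcome is body composition, as measured by air displacement plethysmography (PEAPod").
- **Target difference:** "we are using clinical judgment to determine that a difference in fat free mass z-score" "of 0.5 is clinically significant". The z-score is attributed to a published 2019 dataset, but no figure from it is reported.
- **Sample size:** at alpha 0.05, "with 80% power, 25 infants per group are required".

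The form's prompt beside this answer reads "Define outcomes and describe data analysis, please include a power calculation". The answer names no SD, test, sidedness, covariate adjustment or allowance for losses. Section 10.4, where an attachment could carry them, lists none.

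Three other places bear on the point. Section 8.4 randomises "in a 1:1 allocation ratio". The enrolment table in section 1.08 ends "Racial Categories Total of all Subjects 30 30 60"; its two columns of 30 are females and males, so it supports only the total of 60, which section 11.2 repeats. Section 10.13 says what could follow "If a significant difference can be shown in the study group".

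**The concern.** A sample size for comparing two means needs the difference, alpha, power and the SD. The plan gives the first three and omits the SD, so the reader cannot check the fourth quantity that matters, the number per group. A z-score has SD 1 in its reference population, and on that scale a 0.5 difference normally needs far more than 25 per group.

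This sentence is the sole justification for the size of the trial. If the SD is nearer 1 than 0.62, a true difference of the size the investigators call clinically significant would more likely be missed than found, while a reader would weigh a non-significant result against a claimed 80% power. Section 10.13 states an aspiration rather than a decision rule, but it shows that wider use of the method is expected to turn on whether significance is reached.

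**Working it through.** **Inputs.** Difference δ = 0.5, alpha 0.05, power 80% and n = 25 per group (section 10.3); 1:1 allocation (section 8.4); planned total 60, so 30 per group with no losses (sections 1.08 and 11.2). The SD σ is not given. I assume σ = 1 as the nominal z-score scale and show 0.6 to 1.2. Sidedness is not given, so both are tried. Results are for the two-sample t-test (noncentral t); normal approximations are marked.

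**1. Trying to reproduce 25 at σ = 1.** The normal approximation is n per group = 2σ²(z₁ + z₂)² / δ².
- Two-sided: 2 × (1.960 + 0.842)² / 0.25 = 62.8, so 63. The t-test gives 64.
- One-sided: 2 × (1.645 + 0.842)² / 0.25 = 49.5, so 50. The t-test gives 51.

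Neither gives 25. Dropping the factor 2 from the one-sided formula gives 24.7, which rounds to 25. That is not a valid size for each of two groups, and the document does not show that it was done.

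**2. The SD that would make 25 correct.** The normal approximation is σ = δ / [(z₁ + z₂)√(2/n)].
- Two-sided: 0.5 / (2.802 × √0.08) = 0.631. The t-test gives 0.618.
- One-sided: the t-test gives 0.701.
- At 30 per group: 0.680 two-sided, 0.770 one-sided.

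**3. Power for a 0.5 difference, two-sided t-test.**

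| SD | Power, 25 per group | Power, 30 per group | Difference with 80% power, 25 per group | 95% CI half-width, 25 per group |
|---|---|---|---|---|
| 0.6 | 82% | 89% | 0.485 | 0.34 |
| 0.8 | 58% | 66% | 0.647 | 0.45 |
| 1.0 | 41% | 48% | 0.809 | 0.57 |
| 1.2 | 30% | 35% | 0.970 | 0.68 |

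At 25 per group, power is 70% at SD 0.7 and 49% at SD 0.9. One-sided power at SD 1 is 54%. For 80% two-sided power the need is 42 per group at SD 0.8, 64 at SD 1.0 and 92 at SD 1.2.

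**4. Where the trial becomes uninformative about 0.5.** The CI half-width is t₀.₉₇₅,₄₈ × σ × √(2/25) = 2.011 × 0.283 × σ. It equals 0.5 at σ = 0.879. Power falls below 50% above σ = 0.884. Below about 0.88 neither problem arises.

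**5. Could adjustment rescue it?** To bring a residual SD of 1 down to 0.618, covariates would have to explain 1 − 0.618² = 0.62 of the variance, a correlation of about 0.79. No adjusted analysis is described. The PEAPOD measurement is planned only before discharge (sections 8.4 and 8.6), so there is no baseline value of the outcome to adjust for.

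**The case against.** The strongest reply is that this is an omission and not an error. No stated figure contradicts another. The SD among infants under 1500 g in one NICU, measured when stable and near discharge, need not equal the reference value of 1. At SD 0.6 the plan is adequate, with 82% power. The cited 2019 dataset may contain an SD that supports 25, and it cannot be seen from here. Planned enrolment of 60 also exceeds the 50 required.

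Most of this is fair as a limit on the conclusion. The 41% is one scenario, and the plan is not proven underpowered. But the dataset is cited for the z-score and no SD is reported from it, so the required value of about 0.62 remains unsupported. Enrolling 60 does not close the gap: with no losses, 80% power still needs an SD of 0.68 or less, and power at SD 1 is 48%. A one-sided test does not close it either. Section 11.1 counts accrual as mother/baby couples and section 8.4 allocates twins together, so the number of independent infants per group is itself not exactly fixed. No allowance is made for that or for removals under section 10.6.

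Asking for a confidence-interval reading goes a little beyond supplying the missing inputs, but it follows from the widths shown above.

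**Conclusion.** The concern holds. The statement that 25 per group gives 80% power cannot be derived from what the plan provides. It is true only if the SD of the fat-free-mass z-score is about 0.62 or less (two-sided) or 0.70 or less (one-sided). On the nominal z-score scale, no valid two-group calculation yields 25: the need is 64 per group two-sided or 51 one-sided, and power at 25 is 41% or 54%.

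Confidence is high that the figure is unsupported. The size of any shortfall depends on the unknown SD. The calculations assume equal groups, a common SD, independent infants and no losses. This must be fixed, because the trial's size rests on this figure alone.

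**What to change.** In section 10.3, state the SD with its source, the test and the sidedness. Use SD 1 unless data supporting another value are cited. Replace the power sentence with wording such as:

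> With 25 evaluable infants per group, a two-sided two-sample t-test at alpha 0.05 and an assumed SD of [1.0, or the cited value], the trial has 80% power for a difference of [0.81] z and [41%] power for 0.5 z. Power for 0.5 z is 82% at SD 0.6, 58% at SD 0.8, 41% at SD 1.0 and 30% at SD 1.2. The result will be read from the estimated difference and its 95% CI. A non-significant result will not be taken to exclude a 0.5 z difference unless the CI does.

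The bracketed figures are for SD 1 and must be recomputed if another SD is justified.

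The change is to wording only and needs no extra infants. Unless an SD of about 0.62 or less can be supported, the stated power or detectable difference becomes less favourable, and the investigators may be asked to defend the sample size again. Enlarging the trial to keep 80% power for 0.5 z would be a separate decision.
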